### **1.3.2.1 Hyperglycemia**

Hyperglycemia was the most common adverse event in the CP13-0501 trial (4 patients) and the only grade  $\geq 3$  toxicity (2 patients) observed. Three patients had a better characterization of hyperglycemia. Although known diabetes was an exclusion criteria for participation in the trial, all 3 patients with hyperglycemia had evidence of pre-existing glucose intolerance prior to initiation of the study on retrospective chart review. Increases in blood glucose levels occurred soon after the first dose (in 2 patients), were in the range of 350 mg/dL, and responded to oral hypoglycemic agents (glipizide or glyburide, and/or metformin).

In a phase II trial of another anti-IGF1-R antibody (CP-751,871) given in combination with carboplatin and paclitaxel to 48 patients with lung cancer, grades 3-4 hyperglycemia occurred in 20% of patients (10% grade 3, 10% grade 4). However, there is no published data on further characterization of these hyperglycemic episodes, nor a detailed study of the pathophysiologic processes involved in this adverse event.

Anti-IGF-1R-induced hyperglycemia might occur due to peripheral impaired glucose metabolism or decreased insulin secretion. IGF-1 has hypoglycemic effects *in vivo* in humans, which are thought to be mediated by the IGF-1R in adipose tissue and skeletal muscle and by the IR in the liver (since adults do not express IGF-1R in hepatocytes). In adipose tissue, IGF-1 induces pre-adipocyte differentiation into adipocytes by a mechanism involving PPAR-gamma, whereas in skeletal muscle, IGF-1R activation leads to increased GLUT-4 mediated glucose uptake. In the liver, IGF-1 has been shown to

decrease hepatic glucose production. The role of IGF-1R signaling in insulin production by pancreatic beta-cells has also been recently characterized: both the presence of IR and IGF-1R (and their hybrid receptors) in these cells seems to be necessary for adequate insulin secretion. IGF-1R also seems to play a major role in pancreatic beta-cells survival in the long term.

Due to the complexity of the interactions of the insulin and insulin-like growth factor axis, the pathophysiologic mechanisms of anti-IGF-1R mediated hyperglycemia cannot be readily inferred. *In vivo*, impaired glucose uptake by skeletal muscle and adipose tissue might contribute to hyperglycemia. A compensatory raise in insulin release would be expected, in turn. However, it is unknown whether anti-IGF-1R also decreases insulin secretion due to downregulation of IGF-1R and IGF-1R/IR hybrids in pancreatic beta-cells. Furthermore, the compensatory increase of IGF-1 levels following anti-IGF-1R therapy might counteract some of the hyperglycemic effects by reducing hepatic glucose production. On the other hand, growth hormone also seems to be up-regulated following anti-IGF-1R antibody treatment, which by itself produces hyperglycemic effects. Therefore, a better characterization of the hormonal and metabolic changes following anti-IGF-1R antibody administration to humans is needed.

## **1.4 Rationale**

This trial is a “window of opportunity” study to establish the pharmacodynamic activity of a short, pre-operative course of treatment of cetuximab and/or IMC-A12 in patients with HNSCC. Safety of the combination and its effects on glucose metabolism (with an emphasis on the pathophysiology of hyperglycemia) will also be evaluated.

### **1.4.1 Rationale: cetuximab**

Cetuximab has a well-established and documented history of efficacy and safety in the treatment of HNSCC, both in combination with radiotherapy (for patients with locally advanced disease) and as a single-agent in the treatment of patients with recurrent HNSCC that has progressed on prior platinum-based therapy; the product has been approved by the US FDA for use in these settings. A detailed description of the clinical

findings leading to this approval may be found in Section 1.1. These previous studies support the importance of EGFR-inhibition as a key strategy to improve clinical outcomes in patients with HNSCC.

## **1.4.2 Rationale: IMC-A12**

### **1.4.2.1 Molecular rationale**

IMC-A12 is a fully human monoclonal antibody of the IgG1 subclass that possesses high affinity for IGF-1R receptor and acts as an antagonist of IGF-1 and IGF-2 ligand binding and signaling. IMC-A12 does not bind to or recognize the human insulin receptor. In addition to blockade of ligand binding, mechanistically, this antibody inhibits the IGF-1R pathway by effecting the internalization and degradation of IGF-1R (through a lysosomal pathway), leading to a reduction in surface IGF-1 receptor density on treated or target cells. As a result, IMC-A12 inhibits the proliferation and growth of a variety of human tumor cell lines both in vitro and in vivo. In preclinical study, IMC-A12 inhibited proliferation in the SCC1483 and SCC6 head and neck cancer cell lines (30%-50% of control); minimal (<20% of control) antiproliferative effects were also observed in the SCC1 and SCC22B cell lines. Because IMC-A12 is a fully human IgG1 antibody, it is also capable of inducing antibody dependent cell-mediated cytotoxicity that may inhibit the growth of tumor cells in vivo.

### **1.4.2.2 Clinical rationale**

IMC-A12 has been studied in the clinical setting in two phase 1 trials, one of which has been presented in abstract form (please refer to section 1.3.2). The antibody has been found to be well tolerated, with possible clinical activity against breast cancer, hepatocellular carcinoma, pheochromocytoma, pancreatic carcinoma and lymphangiomatosis (stable disease  $\geq$  4-6 months).

Three other anti-IGF-1R antibodies (AMG-479, CP-751,871, and R1507) have also been studied in humans so far. AMG-479 has shown activity against neuroendocrine

carcinomas (1 partial response and 1 minor response) and Ewing sarcoma (1 complete response) in a phase I study. The agent was also well tolerated, with thrombocytopenia considered dose limiting in one patient. CP-751,871 has been given in combination with carboplatin and paclitaxel in a randomized phase 2 study of patients with non-small cell lung cancer. Response rates were higher in the experimental arm as compared to the chemotherapy-only arm (46 versus 32%, respectively), with 71% of patients with squamous cell carcinoma presenting an objective response. The drug was also well tolerated (dehydration and hyperglycemia were the most common grades 3-4 adverse events and easily manageable). R1507 has been studied in two phase I studies given in different schedules, and has shown activity in Ewing sarcoma (2 partial responses) and disease stabilization in a number of tumor types (including soft tissue sarcomas, non-colorectal gastrointestinal cancer, colorectal cancer, melanoma, prostate cancer, mesothelioma, cervical cancer, and HNSCC). A trend toward increase glucose in serial oral glucose tolerance tests was detected in both studies of R1507. The safety of the antibodies against the IGF-1R receptor, and the early efficacy signals, especially in patients with squamous cell carcinomas, provide clinical rationale for testing IMC-A12 in the treatment of HNSCC.

#### **1.4.2.3 Pharmacokinetics data and dose rationale**

Pharmacokinetics data from the CP13-0501 phase I trial of weekly IMC-A12 indicate that there is a dose-dependant elimination of the drug and non-linear exposure, consistent with a saturable clearance mechanism. After the first administration, minimum serum concentrations of IMC-A12 given at 6 or 10 mg/kg were above 58 mcg/mL 7 days after the initial infusion. At steady-state, the 6 and 10 mg/kg cohorts exhibited a half-life of 209 and 202 hours. The minimum serum concentrations two weeks post- infusion of the drug were 146 and 259 mcg/mL for the 6 and 10 mg/kg doses, respectively.

The target serum concentration for IMC-A12 is hypothesized to be one that maintains IMC-A12 trough concentrations at approximately 58 mcg/mL, which is the threshold level of IMC-A12 that demonstrated inhibition of growth in human tumor xenograft

models in mice. Therefore, the recommended dose for future studies, derived from the CP13-0501 phase I trial, was 6 mg/kg/week, and will be used in this trial as well.

#### **1.4.3 Rationale for combination of cetuximab and IMC-A12 in HNSCC**

The IGF-1R interacts with a variety of structurally distinct receptor families, including the HER family. Crosstalk between the IGF-1R and the EGFR was first identified in murine 3T3 fibroblasts, in which functional IGF-1R signaling is essential for EGF-induced mitogenesis. This effect has been linked to prolonged activation of ERK2. In mammary epithelial organ cultures, IGF-1 stimulated cell cycle progression weakly in the absence of EGF and, by upregulating cyclin E, was found to be essential for EGF-induced progression past the G1-S checkpoint. An EGFR tyrosine kinase inhibitor, gefitinib, was found to block IGF-1-induced ERK1 and ERK2 signaling in the mammary epithelial cell line, HB4A. IGF-1 was found to promote tyrosine phosphorylation of both IGF-1R and EGFR in these cells and increased existing levels of a complex containing both receptors. However, in breast cancer cell lines that all express IGF-1R, an EGFR TKI had no effect on MAPK signaling and IGF-1-induced proliferation was unimpeded in MCF-7 cells, which have a high level of IGF-1R expression. These findings suggest that there is no requirement for a co-receptor to transduce signaling in these fully transformed cells, and therefore that cancer cells could circumvent blockade of EGFR-mediated signaling by increased utilization of the IGF-1R pathway; in such a case, targeting both pathways would be a useful strategy.

Preclinical research has demonstrated a synergistic antitumor effect associated with the combination of cetuximab and agents targeting the IGF-1R in BxPC-3 pancreatic carcinoma xenograft line, HCT-8 colorectal cancer xenografts, GEO xenografts, H226 lung cancer lines, and other cancer cell lines, with no observable side effects versus monotherapy. In many of these cell lines, exposure to EGFR or HER2 inhibitors increases levels of IGF-1R and EGFR or HER2 hetero-oligomers in a protein complex, the nature of which remains to be elucidated. It has also been shown that m-TOR mediated survivin synthesis could rescue lung cancer cells from the effects of erlotinib,

an EGFR TKI, suggesting that signaling through PI3K/AKT is involved in mediating resistance to EGFR inhibitors in this model. As reported in other types of cancer cells, inhibition of IGF-1R restored sensitivity to erlotinib in these cells.

M.D. Anderson investigators have specifically studied the effects of the IGF-1R TKI OSI868, alone and in combination with an EGFR TKI (erlotinib), on HNSCC cell lines. Their data indicate that single agent treatment with OSI868 or erlotinib reduced the viable number of SqCC/Y1 cells with lower levels of pIGF-1R, IGF-1R, and EGFR expression compared to other cell lines. Cells with higher levels of pIGF-1R or EGFR expression showed very mild response to single agent treatment; the antiproliferative effect of combined erlotinib and OSI868 was significantly enhanced in such cells. Ultimately, the combination of erlotinib and OSI868 exhibited significantly enhanced growth inhibition compared to single agent treatment under both hypoxic and normoxic conditions (personal communication, [name], Houston, TX). These observations in preclinical models provide rationale for simultaneous targeting of IGF-1R and EGFR in the clinic.

Currently, a phase II clinical trial of IMC-A12 alone or with cetuximab in patients with platinum-refractory recurrent and/or metastatic HNSCC is accruing at M. D. Anderson Cancer Center. Amendments to this protocol will be submitted should data from that study show any concerns as regards safety of the combination.

#### **1.4.4 Rationale: selection of phospho-Akt modulation as primary endpoint**

Three major intracellular signaling pathways downstream the EGFR are believed to mediate its neoplastic effects: Ras/Raf/MAP-kinase, PI3-kinase/Akt/mTOR and STAT3. The Ras/Raf/MAP-kinase pathway has been implicated in cell proliferation, whereas the PI3-kinase/Akt/mTOR pathway has been implicated in cell survival. Similarly, the two major IGF-1R downstream signaling pathways have been shown to involve Ras/Raf/MAP-kinase and PI3-kinase/Akt/mTOR.

Phosphorylated Akt has been demonstrated to be associated with failure of local disease control by radiation therapy in patients with HNSCC. Moreover, patients with oral cancer harboring high levels of expression of phospho-Akt have a statistically significant inferior disease-free survival, independently of stage and nodal status.

In non-small cell lung cancer, high basal levels of phospho-Akt (but not phospho-MAP-kinase) have been identified as a predictive marker of response in patients treated with the EGFR TKIs. Interestingly, gefitinib-treated patients whose tumors were EGFR positive (independently of the method of EGFR assessment), had a better response rate, disease control rate, time to progression and survival if they had concomitant higher levels of phospho-Akt, as compared to EGFR positive/phospho-Akt negative tumors. The double positive EGFR/phospho-Akt group also had better outcome when compared to the group negative for EGFR and positive for phospho-Akt, indicating that aberrant and not EGFR-dependant phospho-Akt activation may lead to gefitinib resistance. Indeed, Lee et. al demonstrated that IGF-1R dependant Akt phosphorylation is associated with EGFR inhibitor's resistance in lung cancer cell lines, and when phospho-Akt is reduced by IGF-1R blocking, sensitivity to EGFR-targeted drugs is restored. This effect is mediated by mTOR and survivin, both of which are downstream of phospho-Akt. Decreased phospho-Akt levels have also been demonstrated following IGF-1R signaling blockade in HNSCC cell lines, and combining EGFR and IGF-1R inhibitors led to an enhanced decrease in the number of viable cells in vitro, as compared to either drug alone (personal communication, [name], Houston, TX).

Given the fact that phospho-Akt represents a crosstalk point between EGFR and IGF-1R intracellular signaling pathways, is inhibited by drugs targeted to both receptors, and has been implicated in mediating resistance to EGFR-targeted agents in non-small cell lung cancer in vitro, it has been selected as the primary endpoint for this biomarker-driven trial. Nonetheless, there is currently no standard method for assessing molecular response to either cetuximab or IMC-A12 in HNSCC and it is possible that phospho-Akt might not reflect molecular activity of these agents. To overcome this potential problem, modulation of several other biomarkers will be evaluated as secondary endpoints in this study as well.

Of note, biomarker modulation in tumors cells has been observed minutes to days after exposure to the investigational agents in pre-clinical models.

#### **1.4.5 Rationale: selection of biomarkers for secondary endpoints**

Biomarkers chosen as secondary endpoints will be assessed in the following tissues: tumor, skeletal muscle, adipose tissue, and blood.

In the tumor tissue, markers of activation of the EGFR pathway (i.e. EGFR, phospho-EGFR) will be analyzed, so as to determine the activity of cetuximab +/- IMC-A12 upstream of phospho-Akt. Morgillo et al. have demonstrated that IGF-1R transphosphorylates EGFR in an in vitro models. However, the magnitude of this novel mechanism of EGFR activation in vivo, and the ability of IMC-A12 to inhibit this transactivation and, accordingly, the activation of downstream signaling molecules is unknown. Similarly, markers of IGF-1R activation upstream of phospho-Akt (IGF-1R and phospho-IGF-1R) will also be evaluated. Local synthesis of IGF-1 and IGF-2 by cancer cells in response to IGF-1R and/or EGFR inhibition will also be determined, as well as the synthesis of a carrier protein responsible for regulating the bioavailability of IGF to its receptor (i.e., IGFBP-3), and IGF-2R, a nonsignaling IGF-2 binding receptor that has been proposed to act as a sink for free IGF-2. Modulation of these molecules could account for differences in the efficacy of IMC-A12 in regulating Akt phosphorylation in the tumors studied. Expression of survivin and HIF-1 alpha will be determined as a marker of activity downstream of phospho-Akt. The degree of apoptosis (through caspase-3 staining) and proliferation (through Ki-67 staining) after treatment will also be evaluated, as markers of the effects of the targeted agents at the cellular level. Markers of invasiveness and angiogenesis (i.e., CD31, MMP-2, and MMP-9) will also be assessed. Additionally, the phosphorylation status of multiple kinases will be assessed using antibody arrays, as well as micro-RNA and messenger-RNA expression levels using high-throughput microarray chips, and proteomics (using high throughput methods), in an attempt to identify predictive markers of response.

In the blood, the levels of free (i.e., not bound to IGF binding proteins) and total IGF-1, IGF-2 and IGFBP-3 will be evaluated and will be correlated with both toxicity and levels

of apoptosis and proliferation. IGF-1 levels have been previously demonstrated to rise in response to IGF-1R inhibition, but the significance of this phenomenon is yet unknown and could potentially represent a mechanism of resistance to IGF-1R-targeted therapy. Similarly, modulation of circulating IGF-2 and IGFBP-3, as well as modulation of the levels of a panel of 59 cytokines and angiogenic factors measured by available luminex multiplex beads kits (Bio-Plex 27-Plex & 23-Plex Kits [Bio-Rad, Hercules, CA] and Human CVD Biomarker Panel 1 kit [Linco Research, Inc., St, Charles, MO]), VEGF, soluble VEGFR-1, soluble VEGFR-2, osteopontin, and other proteins measured by high-throughput proteomic analysis could also be related with both efficacy and toxicity of cetuximab and/or IMC-A12.

With respect to intermediary metabolism markers, the levels of glucose, insulin, peptide C (which is secreted in equimolar levels to insulin), triglycerides and free fatty acids (which reflect the levels of lypolysis), and fructosamine (a marker of sustained hyperglycemia) will be determined, so as to evaluate the response of insulin secretion and the degree of insulin resistance following IGF-1R inhibition. The mechanisms of potential insulin resistance will also be evaluated, by determining the levels of the insulin receptor, its substrates (i.e. insulin receptor substrate-1) and downstream effectors, and their phosphorylated forms in adipose and skeletal muscle tissues. These sites represent, together with the liver, the main targets of insulin-mediated metabolic regulation. Of note, phosphorylation of the insulin receptor and the insulin receptor substrate-1 in serine sites has been shown to be associated with impaired insulin action in these cells. Glucose transporter-1 and 4 expression, which is up-regulated by insulin and plays a key role in clearing glucose from the blood, will also be determined in skeletal muscle and adipose tissues, as well as the phosphorylation status of multiple kinases (using antibody arrays), micro-RNA and messenger-RNA expression levels (using high-throughput microarray chips), high-throughput proteomic analysis

Since this study represents in essence a biomarker-driven, discovery trial, evaluation of other biomarkers will be performed in the samples obtained, as new knowledge becomes available on the potential mechanisms of action, resistance and toxicity of cetuximab and IMC-A12.

## 2 Study objectives

### 2.1 Primary objective

The primary objective of this study is to assess the degree of modulation of phospho-AKT in HNSCC after a short, pre-operative course of treatment with cetuximab and/or IMC-A12.

### 2.2 Secondary objectives

The secondary objectives of this study are to assess:

1. Safety of cetuximab and/or IMC-A12 (particularly in the pre-operative setting),
2. Effects of IMC-A12 on glucose metabolism (with an emphasis on the pathophysiology of hyperglycemia).
3. Modulation of a panel of biomarkers in HNSCC after treatment with cetuximab and/or IMC-A12 and attempt correlation with clinical outcomes.
4. Objective response to, and histopathological changes after the short course of treatment.

## 3 Patient selection

### 3.1 Study population

Patients will be recruited from a population of HNSCC patients treated at the MDACC, for whom surgical resection of the tumor is indicated as part of the standard treatment plan.

It is anticipated that 60 patients (4/month) will be accrued over a period of 15 months.

### 3.2 Inclusion criteria

Each patient must meet all of the following criteria to be enrolled in this study:

1. The patient has a histologically or cytologically-confirmed diagnosis of squamous cell carcinoma of the head and neck (excluding carcinomas of the nasopharynx types II and III according to the World Health Organization criteria), for whom surgical resection of the tumor is planned as part of the treatment. Patients with skin squamous cell carcinomas of the head and neck region will also be included in this study.
2. There is availability of a baseline, paraffin-embedded, tumor specimen for biomarker evaluation. No anti-neoplastic treatment is allowed between the time from obtaining the baseline tumor specimen and randomization. If a baseline tumor specimen is not available, a biopsy of the tumor will be performed prior to randomization.
3. Prior treatment with biological agents targeted to the epidermal growth factor receptor is allowed, provided the time from last exposure to this treatment was  $\geq$  6 months.
4. The patient has a fasting serum glucose  $<$  130 mg/dL and HbA1C  $\leq$  7.0%. Patients with a history of diabetes mellitus are allowed to participate, provided that they are on a stable dietary or therapeutic regimen for this condition.
5. The patient has adequate renal function, defined by serum creatinine  $\leq$  1.5 x the institutional upper limit of normal (ULN), or creatinine clearance  $\geq$  60 mL/min for patients with creatinine levels above the ULN
6. Because the teratogenicity of cetuximab and IMC-A12 is not known, women of childbearing potential and men must agree to use adequate contraception (hormonal or barrier method of birth control; abstinence) prior to study entry and for the duration of study participation.
7. The patient is age  $\geq$  18 years.
8. The patient or the patient's legally authorized representative has the ability to understand and the willingness to sign a written informed consent document.
9. ECOG performance status of 0-2

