## **8.8 Clinical significance**

### **8.8.1 Pregnancy**

Women of childbearing potential (WOCBP) and fertile men with partners of childbearing potential must be using an adequate method of contraception to avoid pregnancy throughout the study and for up to 4 weeks after the study in such a manner that the risk of pregnancy is minimized.

WOCBP include any female who has experienced menarche and who has not undergone successful surgical sterilization (hysterectomy, bilateral tubal ligation, or bilateral oophorectomy) or is not postmenopausal (defined as amenorrhea  $\geq 12$  consecutive months or women on hormone replacement therapy with documented serum follicle stimulating hormone level  $\geq 35$  mIU/mL). Even women who are using oral, implanted, or injectable contraceptive hormones or mechanical products, such as an intrauterine device or barrier methods (e.g., diaphragm, condoms, spermicides), to prevent pregnancy, are practicing abstinence, or whose partner is sterile (e.g., vasectomy), should be considered to be of childbearing potential.

WOCBP must have a negative serum or urine pregnancy test at baseline. Sexually active WOCBP must use an effective method of birth control during the course of the study, in a manner such that the risk of failure is minimized.

Prior to study enrollment, WOCBP must be advised of the importance of avoiding pregnancy during trial participation and the potential risk factors for an unintentional pregnancy. This discussion will be documented on the informed consent form required for study participation.

In addition, all WOCBP or fertile men with partners of childbearing potential should be instructed to contact the investigator immediately if they suspect they or their partner

might be pregnant (eg, missed or late menstrual period) at any time during study participation.

If following initiation of study treatment, it is subsequently discovered that a trial patient is pregnant or may have been pregnant at the time of exposure to IMC-A12 and/or cetuximab, including during at least 6 half-lives after product administration, IMC-A12 and cetuximab will be permanently discontinued in an appropriate manner.

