## **10.2 Removal of patients from therapy**

A patient should be withdrawn from therapy if, in the opinion of the investigator, it is medically necessary, or if it is the wish of the patient. If the patient does not return for a scheduled visit, every effort should be made to contact the patient; in any circumstance, patient outcome should be documented whenever possible.

A patient should be removed from therapy if:

- Tumor progression occurs, and is confirmed by radiographic progression (not solely based on clinical and/or tumor marker suggestions of progression, unless global deterioration of health status (symptomatic deterioration) requiring discontinuation occurs);
- A grade 4 possible, probable or definite treatment-related toxicity occurs;
- There is toxicity requiring more than 7 days delay of the second treatment dose;
- Other unacceptable toxicity necessitates cessation of treatment;
- The physician feels it is in the best interest of the patient to stop the treatment;
- The patient requests to be removed from the study;
- The patient is lost to follow-up;
- The patient becomes pregnant, or
- The sponsor (MDACC), supporting drug companies (Eli Lilly & Co. and ImClone Systems) or investigator terminates the study.

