### **10.3 *Study completion***

This study will be considered complete when one or more of the following conditions is met:

- All patients have completed all required study visits.
- All patients have discontinued from the study.
- The IRB, Eli Lilly & Co., or ImClone Systems discontinues the study because of safety considerations.

Long-term efficacy and toxicity data may continue to be collected after the study has been completed.

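### The contraception wording is inconsistent, sets no minimum and is not counted from the last dose, so cover is not guaranteed for IMC-A12 patients who leave the study early

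*Combined protocol and SAP*

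**What the plan says.** The protocol states the duration of contraception in three ways.

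- Inclusion criterion 6, in the synopsis and in section 3.2: "prior to study entry and for the duration of study participation". It gives as its reason that the teratogenic risk of both drugs is unknown.
- Section 8.8.1, first paragraph, for women of childbearing potential and for fertile men with partners of childbearing potential: "throughout the study and for up to 4 weeks after the study".
- Section 8.8.1, further down, for sexually active women of childbearing potential: they "must use an effective method of birth control during the course of the study".

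Two other parts of section 8.8.1 bear on the point. Patients are told to call the investigator if they suspect that they or a partner "might be pregnant (eg, missed or late menstrual period) at any time during study participation". When a pregnancy is discovered, the period that counts as possible exposure is described as "including during at least 6 half-lives after product administration".

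The protocol does not define when one patient's participation ends. Section 10.3 defines completion for the whole study, for example "All patients have completed all required study visits". Section 10.2 lists, among its reasons for stopping therapy, "The patient requests to be removed from the study" and "The patient is lost to follow-up".

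**The concern.** A site or a patient can take a different stopping point from each statement, and none refers to the last dose, which is when exposure begins to fall. The words *up to* give a ceiling rather than a floor. The same section nevertheless supplies its own measure of how long exposure may last. If contraception can lapse inside that period, the protocol permits a conception that it would itself class as possibly exposed, with drugs whose teratogenic risk it calls unknown. The instruction to call about a suspected pregnancy is also tied to participation, so the prompt lapses when the patient leaves. Pregnancies that do become known are dealt with in section 8.8.1. The weakness is in prevention and in prompting the call.

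**Working it through.** The protocol gives no day count for its 6-half-life period, so there is no figure of its own to reproduce.

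**Inputs**
- IMC-A12 half-life at steady state: 209 h at the trial dose of 6 mg/kg and 202 h at 10 mg/kg (section 1.4.2.3).
- Exposure period for a discovered pregnancy: at least 6 half-lives (section 8.8.1).
- Adverse event collection: to 30 days after the last dose (section 8.5).
- Post-operative contact: within 30 days after surgery (section 7.4). Surgery must fall within 10 days of the last dose for evaluability (synopsis, section 12.3).
- Repeat audiometry for anyone given IMC-A12: within 90 days after surgery (sections 6.8 and 7.4).
- Post-study period in section 8.8.1: 0 to 28 days.

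**Benchmark period**

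6 x 209 / 24 = 52.25 days (6 x 202 / 24 = 50.5 days at the 10 mg/kg value).

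**Cover under section 8.8.1 with the full 4 weeks**

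Cover = days from last dose to end of participation + 28. The end of participation is my assumption, because the protocol does not define it. Day 30 is the end of adverse event collection. Day 40 is 10 + 30, the latest post-operative contact in an evaluable patient. Day 100 is 10 + 90, the latest audiometry. Days 0, 7 and 14 represent leaving the study early. The last column is the rule proposed under the fix, max(56, days to end of participation + 28).

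| Participation ends (days after last dose) | Cover, 8.8.1 (days) | Against 52.25 | Proposed rule (days) |
|---|---|---|---|
| 0 | 28 | 24.25 short | 56 |
| 7 | 35 | 17.25 short | 56 |
| 14 | 42 | 10.25 short | 56 |
| 30 | 58 | covered | 58 |
| 40 | 68 | covered | 68 |
| 100 | 128 | covered | 128 |

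With the full 4 weeks, the benchmark is met once participation lasts 52.25 - 28 = 24.25 days after the last dose.

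**Effect of reading *up to* as less than 4 weeks**

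A patient followed to day 30 still needs 52.25 - 30 = 22.25 further days. Any reading shorter than that leaves even this patient short.

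**Sensitivity to the half-life**

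Section 1.4.2.3 describes saturable clearance, and no half-life is given for 2 or 3 doses. For a patient who leaves on the dosing day, 28 days spans 6 half-lives only if the half-life is 28 x 24 / 6 = 112 h or less. The proposed 56 days spans them up to 56 x 24 / 6 = 224 h. No cetuximab half-life is given, so no period can be computed for arm A.

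**The case against.** The strongest reply is that the statements differ in length without contradicting one another. Inclusion 6 is what a patient agrees to at entry, section 8.8.1 is the stricter conduct rule, and section 13.3 obliges the investigator to meet every requirement. This stands. A reader might infer from inclusion 6 alone that patients whose participation ends 30 to 40 days after the last dose are 22 to 12 days short (52.25 - 30 and 52.25 - 40). The documents do not support that, because section 8.8.1 applies as well.

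Secondly, stopping therapy is not leaving the study. Patients with grade 3 or 4 IMC-A12 infusion reactions are still followed (section 9.2.1), and everyone given IMC-A12 is due audiometry after surgery. This also stands, and it confines the withdrawal gap to patients who leave the study itself. The audiometry sets no minimum, since it may be done early or missed by a patient who has gone.

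Thirdly, section 8.8.1 runs from the end of the study, and section 10.3 defines that only for the study as a whole, with accrual expected over 15 months (section 3.1). Read that way, nearly every early leaver is covered well beyond 52 days. The reading is possible, so the early-withdrawal shortfalls depend on a per-patient reading. But a rule whose length turns on when other patients finish gives an individual no usable date.

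Finally, 6 half-lives is an exposure definition for a discovered pregnancy and not a contraception requirement. That is correct, and it is used here only as a benchmark.

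**Conclusion.** The point holds as a minor patient-safety correction. The wording is inconsistent, has no floor and is not anchored to the last dose. A patient who stays to 30 days after the last dose and uses the full 4 weeks is covered. Cover is not guaranteed in two situations: leaving the study early, where it is 28 to 42 days for departure 0 to 14 days after the last dose, or 24 to 10 days below the benchmark; and any reading of *up to* as materially less than 4 weeks.

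This rests on the steady-state half-life of 209 h, on 6 half-lives as the benchmark, and on a per-patient reading of when the study ends. A shorter half-life after 2 or 3 doses would shrink the gap, and at 112 h or below the full 4 weeks would be enough in every case.

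A reader might take the 40 patients planned for arms B and C (20 + 20) as the number at risk. The documents do not support that. Only those of reproductive potential who leave early, or who stop contraception early, are concerned, and their number is not estimated but is likely to be small. Nor can it be said that patients are misinformed, since the consent wording is not in the reviewed copy. The primary endpoint, type I error and power are unaffected.

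**What to change.** Use one rule in the synopsis, section 3.2 item 6 and section 8.8.1: contraception, and prompt contact about a suspected pregnancy, for at least 8 weeks after the last dose of study drug or until 4 weeks after the end of the patient's participation, whichever is later. State that it also applies after early withdrawal, replace *up to* with *at least*, and define the end of participation for the individual patient. The second limb keeps the rule from ever being shorter than the full 4 weeks of section 8.8.1. Apply it to all three arms for simplicity, unless a cetuximab half-life is added that supports a different period, and match the consent discussion to it.

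The cost is wording in the protocol and, where needed, the consent form. No visits, tests or patients are added. The downside is a slightly longer contraception requirement for some patients, mainly those who withdraw early.
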